3.1.3 Guidelines for Administration

Panobinostat (FARYDAK) should be taken orally once on each scheduled day at about the same time, either with or without food.

Panobinostat capsules should be swallowed whole with a cup of water. Do not open, crush, or chew the capsules.

If a dose is missed it can be taken up to 12 hours after the specified dose time. If vomiting occurs the patient should not repeat the dose but should take the next usual scheduled dose.

3.1.4 Risks Associated with Panobinostat

The most common adverse reactions (incidence of at least 20%) in clinical studies are diarrhea, fatigue, nausea, peripheral edema, decreased appetite, pyrexia, and vomiting.

The most common non-hematologic laboratory abnormalities (incidence $\geq 40\%$) are: Hypophosphatemia, hypokalemia, hyponatremia, and increased creatinine.

The most common hematologic laboratory abnormalities (incidence $\geq 60\%$) are: thrombocytopenia, lymphopenia, leukopenia, neutropenia, and anemia.

Panobinostat carries a boxed warning alerting patients and health care professionals that severe diarrhea and severe and fatal cardiac events, arrhythmias and electrocardiogram (ECG) changes have occurred in patients receiving Panobinostat.

Other notable adverse drug reactions of Panobinostat not described above, which were either clinically significant, or occurred with a frequency less than 10% but had a frequency in the Panobinostat arm greater than 2% over the control arm in the multiple myeloma clinical trial are listed below:

Infections and infestations: hepatitis B.

Endocrine disorders: hypothyroidism.

Metabolism and nutrition disorders: hyperglycemia, dehydration, fluid retention, hyperuricemia, hypomagnesemia.

Nervous system disorders: dizziness, headache, syncope, tremor, dysgeusia.

Cardiac disorders: palpitations.

Vascular disorders: hypotension, hypertension, orthostatic hypotension.

Respiratory, thoracic and mediastinal disorders: cough, dyspnea, respiratory failure, rales, wheezing.

Gastrointestinal disorders: abdominal pain, dyspepsia, gastritis, cheilitis, abdominal distension, dry mouth, flatulence, colitis, gastrointestinal pain.

Skin and subcutaneous disorders: skin lesions, rash, erythema.

Musculoskeletal and connective tissue disorders: joint swelling.

Renal and urinary disorders: renal failure, urinary incontinence.

General disorders and administration site conditions: chills.

Investigations: blood urea increased, glomerular filtration rate decreased, blood alkaline phosphatase increased.

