6. STUDY OBJECTIVES

6.1 Primary Objective

The primary objective of this study is to evaluate the feasibility of safely opening the BBB in children with progressive DMG treated with oral Panobinostat using FUS with DEFINITY® microbubbles and neuro-navigator-controlled sonication.

With the current study we are planning to evaluate the safety and feasibility of using FUS and open-space neuronavigator-controlled sonication to open one, two or three tumor sites. For the purpose of the study we will be administering oral Panobinostat in children with progressive DMG. This drug has a known toxicity profile, dose and well documented efficacy against many metastatic cancers. Successful opening and closing of the BBB will be confirmed with periodic MRIs.

Safety will be assessed by evaluation of physical and neurologic examinations, laboratory studies, radiographic studies, and by adverse events as per the CTCAE version 5.0. An adverse event is

any new or worsening symptom or clinical finding which occurs during the study period. Adverse events are to be recorded irrespective of causality on the adverse event form. Each event will be described by its severity (mild, moderate, severe, life-threatening), duration, and relation to the study medication (unrelated, unlikely, possible, probable, and definite).

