11.2 Recording of Suspected Adverse Reactions (SARs) and Adverse Device Effects (ADEs)

All observed or volunteered adverse effects (serious or non-serious) and abnormal test findings, regardless of treatment group, if applicable, or suspected causal relationship to the investigational products or, if applicable, other study treatment or diagnostic product(s) will be recorded in the subjects' case histories. For all adverse effects, sufficient information will be pursued and/or obtained so as to permit 1) an adequate determination of the outcome of the effect (i.e., whether the effect should be classified as a serious adverse effect) and; 2) an assessment of the causal relationship between the adverse effect and the investigational products or, if applicable, the other study treatment or diagnostic product(s).

Adverse effects or abnormal test findings felt to be associated with the investigational device or, if applicable, other study treatment or diagnostic product(s) will be followed until the effect (or its sequelae) or the abnormal test finding resolves or stabilizes at a level acceptable to the sponsor-investigator.

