12.2 Dose Limiting Toxicities

Dose limiting toxicities (DLT) will be defined as any new (or increased from baseline), treatment related (drug and/or device):

1. Neurological deficits based on neurological examination which are grade 3 or greater nervous system adverse events at least possibly attributed to sonication (as defined by CTCAE v5.0).

2. Grade 2 or higher symptomatic intracranial hemorrhage or stroke.

These deficits include but are not limited to changes in level of consciousness, new onset speech difficulties (aphasia, mutism, dysarthria), confusion, visual field deficits, focal weakness, seizures. The DLT period is defined as starting the day of the first scheduled FUS treatment and lasting until 14 days after the last scheduled FUS treatment.

Furthermore, DLT criteria include any systemic treatment- related Grade 3 or higher hematologic or non-hematologic toxicity within a period of 14 days after the scheduled FUS treatment. Examples of exceptions could include:

- I. Grade 3 thrombocytopenia without bleeding, Grade 3 or 4 lymphopenia, Grade 3 neutropenia without fever.
- II. Nausea, vomiting or diarrhea responding to medical management within 48 hours
- III. Electrolyte disturbances that are asymptomatic and response to supportive care within 48 hours; hyperglycemia \leq 12 hours

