Appendix A- Sequence of Events

An enumerated list of chronological study procedures has been provided below. Please see Appendix B for a table version.

Pre-study (up to 7 days before the NgFUS procedure):

1. Patient Recruited
2. Enrollment Criteria Verified
3. Informed Consent Signed
4. MRI with and without IV Gadolinium contrast (A recent (no longer than 7 days prior to the time of the procedure) MRI with and without Gadolinium contrast that includes T1, T2, and FLAIR is required, otherwise the MRI will have to be repeated).
5. Pre-Study Information Collected
 - a. Medical History
 - b. Physical Exam
 - c. Vital Signs
 - d. Height
 - e. Weight
 - f. Karnofsky/Lansky Performance Status
 - g. Neurocognitive Assessment Performed
 - h. Basic labs/pre-op Testing Collected and Reviewed
 - i. CBC with differential
 - ii. Serum Chemistry (BMP and hepatic function panel)
 - iii. Coagulation Panel (PT, INR, APTT)
6. Subject starts treatment.

NgFUS Procedure:

Subjects will be assigned a NOTS (number of tumor sites) level pertaining to the number of tumor sites FUS treatment will be applied to as laid out in [Section 7.2](#).

Panobinostat Treatment Schedule:

- 1 cycle of Panobinostat= 2 weeks of 3 alternate treatment days. Subjects will undergo 6 cycles spaced 1 week apart.
- In each cycle, subjects will receive Focused Ultrasound (NgFUS) and injection of DEFINITY® microbubbles using NgFUS system in the Radiation Oncology Suite on Days 1, 3, and 5 (all treatment days).
- **MRI to Determine Opening of Blood Brain Barrier:** During Week 1 Day 1 of each cycle, 2-4 hours post FUS treatment with DEFINITY® microbubbles on Day 1, subjects will receive an MRI with injection of Gadolinium contrast.

Post NgFUS Procedure (+4-24 hours):

Panobinostat Treatment Schedule:

- Treatment includes receiving Oral Panobinostat at 15 mg/m².
- **MRI to Confirm Closure of Blood Brain Barrier:** On Week 1 Day 3 of every other cycle (Cycles 1, 3 and 5), 24-48 hours post Day 1 FUS treatment with DEFINITY® microbubbles, subjects will undergo MRI with gadolinium pre Day 3 FUS treatment to ensure closure of the blood brain barrier.
- A NOTS escalation scheme for the number of tumor sites targeted by FUS will be followed as laid out in [section 7.2](#). As stated in the section, an MRI (without contrast) will be performed prior to each escalation to clear the subject of any possible DLTs and increase in tumor size.

Follow-up Period (until 90 days after treatment):

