Appendix B- Study Calendar

- 1 cycle of Panobinostat= 2 weeks of 3 alternate treatment days. Subjects will undergo 6 cycles, each spaced 1 week apart.
- In each cycle, subjects will receive Focused Ultrasound (NgFUS) and injection of DEFINITY® microbubbles and using NgFUS system in the Radiation Oncology Suite on Days 1, 3, and 5 (all treatment days).

| | Screening | Treatment Phase | | | | Follow-up |
|--------------------------------------------------|------------------|------------------------|---------------------|----------------|----------------|------------------|
| Time points | -7 days | Day 1 | +12-+48hours | Day +3 | Day +5 | +90 days |
| Height | X | | | | | X |
| Weight | X | | | | | X |
| Medical History | X | | | | | |
| Demographics | X | | | | | |
| Vital signs | X | | | | | X |
| Informed Consent | X | | | | | |
| CBC w/diff, plts | X | | X ^c | | | X |
| Serum chemistry (BMP and hepatic function panel) | X | | X ^d | | | X |
| Coagulation Panel (PT, INR, PTT) | X | | X ^e | | | |
| Concomitant Medication Review | X | | | | | X |
| EKG | X | | X ^f | | | |
| Focused Ultrasound Treatment | | X ^b | | X ^b | X ^b | |
| Performance Status | X | X | | | | X |
| MRI | X ^a | | X ^g | X ⁱ | | X ^j |
| Oral Panobinostat | | X ^h | | X ^h | X ^h | |
| Physical Exam | | | X ^k | | | |

a- MRI with gadolinium contrast to be performed for screening purposes.

b- In each cycle, subjects will receive Focused Ultrasound (NgFUS) and injection of Microbubbles using NgFUS system in the Radiation Oncology Suite on Days 1, 3, and 5 (all treatment days).

c- Perform one approximately 12-24 hours post NgFUS

d- Perform once approximately 12-24 hours post NgFUS

e- Perform once approximately 12-24 hours post NgFUS.

f- An electrocardiogram (EKG) will be performed once approximately 12—48 hours post NgFUS.

g- **MRI to Determine Opening of Blood Brain Barrier:** During Week 1 Day 1 of each cycle, 2-4 hours post FUS treatment with Microbubbles on Day 1, subjects will receive an MRI with injection of Gadolinium contrast.

h- Treatment includes receiving Oral Panobinostat at 15 mg/m².

i- **MRI to Confirm Closure of Blood Brain Barrier:** On Week 1 Day 3 of every other cycle (Cycles 1, 3 and 5), 24-48 hours post Day 1 FUS treatment with Microbubbles, subjects will undergo MRI with gadolinium pre Day 3 FUS treatment to ensure closure of the blood brain barrier.

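### Hypophosphatemia is a named common panobinostat abnormality, but the scheduled chemistry does not appear to measure phosphate, so a low or zero count cannot be read as absence

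*Combined protocol and SAP*

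**What the plan says.** Section 3.1.4 (Risks Associated with Panobinostat) sets out two groups of common laboratory abnormalities. The non-hematologic group, at 40% or more, is "Hypophosphatemia, hypokalemia, hyponatremia, and increased creatinine". The hematologic group, at 60% or more, has five blood-count abnormalities. A separate list of other notable reactions includes "hyperglycemia, dehydration, fluid retention, hyperuricemia, hypomagnesemia".

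The tests are fixed in two places. Appendix A, item 5h, asks before treatment for "Serum Chemistry (BMP and hepatic function panel". The Appendix B calendar row is "Serum chemistry (BMP and hepatic function panel", marked at screening, in the post-treatment column and at +90 days. Note d to that row reads "Perform once approximately 12-24 hours post NgFUS". Phosphate and magnesium are not named as tests anywhere in the documents, including the eligibility laboratory criteria in 8.1.2.

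Laboratory results matter to the primary question. The synopsis names laboratory studies as an outcome measure for the primary endpoint, and 6.1 states: "Safety will be assessed by evaluation of physical and neurologic examinations, laboratory studies". Section 12.2 counts treatment-related systemic toxicity of Grade 3 or higher as a DLT. Among its example exceptions is "Electrolyte disturbances that are asymptomatic and response to supportive care within 48 hours".

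**The concern.** The protocol names a frequent laboratory toxicity of the study drug, and its own schedule has no test for it. If phosphate is not measured, low values without symptoms will mostly go unseen. The adverse event frequencies planned in 10.2 could then show few or no cases, and a reader could take that as reassurance.

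The safety rules have the same gap. The electrolyte exception in 12.2 turns on whether a disturbance is asymptomatic and how fast it responds. An asymptomatic disturbance is found only by measuring it, so for phosphate neither the Grade 3 rule nor its exception can be applied in the same way to every subject. Under 7.2 and 12.1 one DLT takes a subject off study, and two at the same NOTS level halt enrollment. The provision in 12.1 on unresolved Grade 2 or higher toxicity is affected likewise.

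The issue is which analytes are measured. Drawing the same panel more often would not close the gap.

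**Working it through.** The plan states no figure on this point, so there is none to reproduce. The check is a comparison of sections, followed by a calculation for scale.

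**Step 1. Named abnormalities against scheduled tests.** Section 3.1.4 names 4 + 5 = 9 most-common laboratory abnormalities.

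| Abnormality (3.1.4) | Scheduled test (Appendix B) |
|---|---|
| Thrombocytopenia, lymphopenia, leukopenia, neutropenia, anemia | CBC with differential and platelets |
| Hypokalemia, hyponatremia, increased creatinine | BMP |
| Hypophosphatemia | None |

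Eight of the nine have a scheduled test. Hypophosphatemia alone does not, and no reason is given for leaving it out. The table assumes standard panel contents. A BMP is taken as sodium, potassium, chloride, bicarbonate, urea, creatinine, glucose and calcium, and a hepatic panel as enzymes, bilirubin and proteins. The documents do not list these, and a local panel could differ.

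**Step 2. Other routes into the record.** Section 11.1 captures all CTCAE adverse events during treatment and for 30 days after. Section 11.2 records abnormal test findings without limiting them to calendar tests. A low phosphate found in routine care would therefore be recorded. The result is under-ascertainment and not a forced zero.

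**Step 3. Scale.** Let n be the number of subjects and p the true incidence, with subjects independent. Expected cases are n × p, and the probability of truly no cases is (1 − p)^n. Section 10.1 gives n from 3 to 15 and mentions 6. The value p = 0.40 is the lower bound in 3.1.4, assumed to carry over. The values 0.20 and 0.10 are assumed lower alternatives.

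| p | n = 3 | n = 6 | n = 15 |
|---|---|---|---|
| 0.40: expected cases | 1.2 | 2.4 | 6.0 |
| 0.40: P(no true case) | 0.6^3 = 0.216 | 0.6^6 = 0.047 | 0.6^15 = 0.0005 |
| 0.20: P(no true case) | 0.8^3 = 0.512 | 0.8^6 = 0.262 | 0.8^15 = 0.035 |
| 0.10: P(no true case) | 0.9^3 = 0.729 | 0.9^6 = 0.531 | 0.9^15 = 0.206 |

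These are probabilities about true cases, not detected ones. With 15 subjects and 40%, a reported zero would almost certainly reflect what was tested. With 3 subjects, or at 10%, a true zero is quite plausible, but without measurement it cannot be told apart from a missed case.

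**The case against.** A reader might infer that the trial must report zero cases by construction. The documents do not support that. Section 11.2 covers "All observed or volunteered adverse effects (serious or non-serious) and abnormal test findings", and 11.1 captures all CTCAE events, so off-schedule results and symptomatic cases would be recorded. Nor does 10.2 define a laboratory safety table; it promises only frequencies and proportions of events such as adverse events.

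Other objections also stand:

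- The 40% is a description of known drug risk, given without a grade split or testing schedule. The trial disease named in 3.1.4 is multiple myeloma. It is not a forecast for children with DMG, and it says nothing about Grade 3 or higher events.
- The 40% applies to phosphate only. Hypomagnesemia appears among the other notable reactions, so no figure here covers it.
- It is tempting to say that without a baseline value no phosphate DLT could be called new. In 12.2 the wording on new or increased findings introduces the neurological and hemorrhage or stroke items; the systemic clause asks only that toxicity be treatment-related. Baseline matters instead through 11.1, which uses the pre-treatment work-up to identify pre-existing conditions.
- A link to the boxed warning on arrhythmia is also tempting, but 3.1.4 does not tie those events to electrolytes.
- Note d may mean a single on-treatment draw. Adding phosphate to it would not recover every case.
- The trial escalates the number of sonicated sites, and 6.1 describes the drug's toxicity profile as known. The point does not touch BBB opening.

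These limit the size of the concern. They do not remove the mismatch between 3.1.4 and the appendices.

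**Conclusion.** The concern holds in a limited form. Followed as written, the plan does not systematically assess hypophosphatemia, the one most-common laboratory abnormality in 3.1.4 with no scheduled test. Its frequency will be under-ascertained, a low or zero count is not evidence of absence, and the systemic DLT rule with its electrolyte exception cannot be applied to it uniformly.

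The conclusion rests on standard panel contents. If the local BMP or hepatic panel does include phosphate, naming the analytes in the protocol settles the matter. The scale rests on the further assumption that the quoted incidence carries over. On that basis a true zero is very unlikely with 15 subjects but not with 3, and at an assumed 10% it is unremarkable at any planned size. The gap should be closed because laboratory studies are part of the primary safety assessment and the remedy is small.

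**What to change.** In Appendix A item 5h and the Appendix B serum chemistry row, add phosphate to the panel at screening and at each scheduled chemistry draw, and include it in the adverse event frequency summary under 10.2. Magnesium can be added on the same sample as an option. If the panels stay as they are, state in the analysis and report that phosphate and magnesium were not systematically assessed, so that a low count is not read as absence.

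The cost is a low-cost assay on blood already being drawn (a second if magnesium is included) and more low-grade adverse events to record. Cases arising and resolving between scheduled draws may still be missed, and the report should say so.

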3.2 Gadolinium

3.2.1 Source and Pharmacology

Gadolinium based contrast agents are derived from Gadolinium is an element with atomic symbol Gd, atomic number 64, and atomic weight 157.25.

3.2.2 Formulation and Stability

Storage requirement

The original gadolinium solution will be stored in the Radiology at a temperature of 20- 25° C as part of standard procedures.

3.2.3 Guidelines for Administration

Gadolinium-based MRI contrast agent is administered intravenously in approximately, 0.2 mL/kg (0.1 mmoles/ kg) at a rate of 10 mL per 15 seconds.

3.2.4 Potential adverse effects

IV administered gadolinium-based contrast agents have been identified as the cause of the rare disease nephrogenic systemic fibrosis (NSF), which presents as acute to subacute edema of the extremities as well as cutaneous plaques[46]. NSF can also be associated with extremity pain and muscle contractures and can lead to severe disability and even death. Development of NSF after gadolinium administration has been linked to renal impairment, with prevalence of 2-6% in patients with severe renal dysfunction[46]. Nevertheless, patients in this study will be screened for appropriate renal function. As with any medication, there is risk of allergic reaction and possible anaphylaxis with administration of gadolinium. Patient's will be monitored for allergic reactions and treated appropriately if any evidence of allergy is identified. Patient's with known pre-existing contrast allergies will be excluded from participation in the study.

4. MICROBUBBLES

4.1 General Information

DEFINITY® microbubbles are FDA-approved for use in adults (NDA 21-064) and are routinely used in ultrasound imaging applications, such as echocardiography or renal imaging, for over 15 years. In the proposed study, we will use the clinically recommended dose of 10 μ l/kg introduced by intravenous bolus injection followed by a 10 ml saline flush, according to the manufacturer's guidelines. More information on the formulation and stability of DEFINITY® microbubbles are included in Appendix 8.1.

4.2 Packaging

New packages of DEFINITY® microbubbles will be shipped from Lantheus Medical Imaging Inc. and will be used in conjunction with the ultrasound transducer to temporarily open the BBB. DEFINITY® microbubbles will be freshly activated before sonication and will be withdrawn using a 1-ml syringe to reach the clinical dose (10 μ l/kg) right before the IV injection.

4.3 Potential Risks

All the potential adverse reactions and their incidence rate can be found in the DEFINITY® safety datasheets. There have been reported side effects such as cardiopulmonary reactions, injection site reaction, back/renal pain, chest pain, dizziness, headache, nausea. Other possible risks during the procedure include bruising at the injection site and hypersensitivity or allergic reaction to

DEFINITY® microbubbles and/or gadolinium injections. For further information on DEFINITY® Microbubbles and their adverse events please see appendix 8.1 attached.

5. FOCUSED ULTRASOUND

5.1 Device Description

The system consists of two main parts: (i) ultrasound unit for sonication and real-time passive acoustic monitoring (Sonic Concepts) and (ii) neuro-navigator (Rogue Research) providing real-time guidance. The clinical FUS transducer will be driven by a function generator (33500B Series, Agilent Technologies, Santa Clara, CA, USA) through a 55-dB radiofrequency power amplifier (A150, E&I, Rochester, NY, USA). A water degassing system (WDS105+, Sonic Concepts) will be used to fill the transducer cone with degassed water and inflate or deflate the cone according to the sonicated location. Finally, microbubble acoustic emissions will be recorded (sampling frequency: 50 MHz, capture length: 10 ms) with a 1.5-MHz passive cavitation detector (PCD; diameter: 32 mm, focal depth: 114 mm, ndtXducer, Northborough, MA, USA).

The neuronavigation guidance is achieved by registration of the physical space to the preloaded MRI that is displayed on the screen. The registration is achieved by the infrared camera reflecting the position of the subject tracker secured close to the brain. The transducer with a passive cavitation detector embedded is attached on the mechanical arm and the position varies depending on the brain structure to be sonicated. The transducer carries a tool tracker so its relative position to the brain can be seen on the screen. Once the transducer is locked at the position of interest the sonication begins. Real time monitoring of microbubble activity during sonication will be achieved via passive acoustic detection. This investigative device will be operated in conjunction with DEFINITY® administered intravenously at the FDA-approved dose.

